Note: Individuals with a well-established DSM-IV diagnosis of autistic disorder, Asperger's disorder, or pervasive developmental disorder not otherwise specified should be given the diagnosis of autism spectrum disorder. Individuals who have marked deficits in social communication, but whose symptoms do not otherwise meet criteria for autism spectrum disorder, should be evaluated for social (pragmatic) communication disorder.

Specify if:

- With or without accompanying intellectual impairment
- With or without accompanying language impairment
- Associated with a known medical or genetic condition or environmental factor
- Associated with another neurodevelopmental, mental, or behavioral disorder
- With catatonia

Project Goals

The goal of the proposed study is to evaluate the safety and feasibility of oral Glutathione in children and adolescents who have Autism Spectrum Disorder. Twenty-four subjects with ASD will receive 12 weeks of oral Glutathione reduced. The hypothesis to be tested is that: Oral Glutathione will be effective in increasing the blood level of Glutathione, which may help to decrease some problem behaviors and irritability in this particular ASD population. The second aim of this study is to evaluate the tolerability of oral Glutathione. The proposed study may provide needed data for future studies aimed at the treatment of aggressive behaviors that can be seen in this patient population.

Background and Significance

Autism Spectrum Disorder is a complex neurodevelopmental disorder, which can involve impaired social interaction, impaired language and communication, limited interest, repetitive/ritualistic behaviors and sometimes aggressive behavior (3). Although Autism Spectrum Disorder has been described in medical literature for years, it remains poorly understood and the exact etiology and neurobiology are not quite clear. However, an emerging topic in research is the imbalance between bodily oxidative systems and anti-oxidative stress in Autism Spectrum cases (i.e. redox systems). Glutathione is involved in neuro-protection against oxidative stress and play a major role in our anti-oxidative stress systems, which may mean that decreasing oxidative stress over time could be a possible treatment for some problem behaviors that are seen in Autism Spectrum Disorder (3).

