N-acetylcysteine is an antioxidant agent and glutamatergic modulator, it is also a precursor to Glutathione via cysteine production. Glutathione is found naturally in the human body and produced by the liver; it is a 3-amino acid (tripeptide) that is composed of cysteine linked to glutamate and followed by glycine attachment (Figure 1). When N-acetylcysteine is de-acetylated, cysteine is provided to feed into the transsulfuration pathway, leading to the production of Glutathione (9). Glutathione is also found in plants, all mammalian tissue, fungi and some bacteria; and it is considered a key determinant of redox signaling, vital in detoxification of xenobiotics, regulates cell proliferation, apoptosis and immune function (6, 7). As mentioned, there is some evidence that antioxidant agents may be beneficial in reducing irritability or aggression in children with ASD. Therefore, we believe that by testing the feasibility of using oral Glutathione directly, and examining the anticipated changes in Glutathione blood level, as we are bypassing the transsulfuration pathway and providing Glutathione supplementation to the body, may be beneficial for ASD patients. Given that Glutathione may have various advantages over other pharmacological agents in treating children with ASD, and it is an all-natural supplement, it can be a promising treatment for irritability and problem behaviors seen in this population and may play a role in correcting the lower levels of plasma reduced Glutathione often observed in children with ASD.

Figure 1: Image NAC de-acetylation and formation of Glutathione (9)

Aims

- 1) To determine whether Glutathione given over a 12-week period increases plasma Glutathione level in a sample of 24 children aged 4-17 years old with a history of Autism Spectrum Disorder.
- 2) To determine the feasibility of using oral Glutathione in this patient population
- 3) To test whether oral administration of Glutathione supplement is well tolerated as a medical food in children with ASD.

Overall, we will examine the effects of Glutathione in children with Autism Spectrum Disorder. Evidence suggests that Glutathione may reduce reactive oxygen species that can accumulate in patients with ASD and thereby may help to decrease significant problem behaviors seen in this population. We hypothesize that oral Glutathione will be safe and well tolerated in patients with Autism Spectrum Disorder.

METHODS

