The study will consist of **12 weeks of open label trial** with treatment of oral Glutathione in 24 subjects with ASD; the subjects will be recruited at the University of Chicago. Subjects will be seen every two weeks for the first month and then every four weeks for the remaining two months with one final visit at the end of the study for a total of 5 visits.

Study Location

This is a single-site trial in the United States, with a total of 24 subjects aged 4-17. The Principal

Page 6 of 17 IRB19-0017 Version 2; date: 4/11/19 Investigator for this study is:

[name]. Professor of Child and Adolescent Psychiatry University of Chicago [name]

All subjects will be seen in the Department of Child and Adolescent Psychiatry at the University of Chicago Medical Center at [name]. The offices are connected to the Department of Psychiatry and provide confidential interview rooms and facilities.

Investigational Agent

Glutathione (GSH) Reduced (Oral Capsules - Jarrow Brand)

- for patients 40kg or less: 500 mg by mouth twice a day for two weeks, then 1000 mg by mouth twice a day for ten weeks.
- for patients greater than 40 kg: 500 mg by mouth twice a day for two weeks, then 1000 mg by mouth twice a day for two weeks, then 1000 mg by mouth each morning and 2000 mg by mouth every afternoon for eight weeks.
- Dosages will be increased based on tolerability and the monitoring of any potential GI side effects as determined by the investigator.

Dosing Regimen for ≤40kg group (BID dosing throughout study)

Week 0 (Visit 1) – Week 2 (Visit 2): 1000mg/day (500mg po qam and 500mg po qpm)
Week 2 (V2) – Week 12 (V5): 2000mg/day (1000mg po qam and 1000mg po qpm)

Dosing Regimen for ≥40kg group (BID dosing throughout study)

 Week 0 (Visit 1) – Week 2 (Visit 2):
 1000mg/day (500mg po qam and 500mg po qpm)

 Week 2 (V2) – Week 4 (V3):
 2000mg/day (1000mg po qam and 1000mg po qpm)

 Week 4 (V3) – Week 12 (V5):
 3000mg/day (1000mg po qam and 2000mg po qpm)

Maximum Amount of Study Drug Needed

V1: 1000mg = 2 (500mg) pills x 14 days = 28 pills V2: 2000mg = 4 (500mg) pills x 14 days = 56 pills V3: 3000mg = 6 (500mg) pills x 28 days = 168 pills V4: 3000mg = 6 (500mg) pills x 28 days = 168 pills

V5: none dispensed (end of study) total per subject: 420 pills

TOTAL PILLS for 24 subjects = \sim 10,080pills maximum (based on recruiting patients \geq 40kg)

SUMMARY OF DATA COLLECTION AND STUDY PROCEDURES BY VISIT							

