		Visit					

Page 7 of 17 IRB19-0017 Version 2; date: 4/11/19

	Screening	1	2	3	4	5	6			
Consent Forms:	Х									
Medical Procedures on Child										
Blood draw		Х					Х			
Heart rate		х	Х	Х	Х	Х	Х			
Blood pressure		х	Х	Х	Х	Х	Х			
		Pare	nt Reports	on Child						
Aberrant Child Checklist	Х	Х	Х	Х	Х	Х	Х			
Social responsiveness Scale	Х	Х	Х	х	х	х	х			
Clinical Global Impression Scale	Х	Х	Х	Х	Х	Х	Х			
PRAS ASD	Х						Х			
Vineland-3	Х						Х			
Side effects checklist		Х	Х	Х	Х	Х	Х			

Subject Recruitment

All potential subjects for this study will be recruited through the Child and Adolescent Psychiatry Department Neurodevelopmental clinic and by Neuropsychological referral.

Subjects:

Inclusion criteria:

- 1) Boys and girls ages 4-17;
- 2) Current diagnosis of Autism Spectrum Disorder as determined by criteria in DSM-5
- 3) Parents of Children ages 4-17 with a current diagnosis of Autism Spectrum Disorder as determined by criteria in DSM-5

Exclusion criteria:

- 1) Unstable medical illness or clinically significant abnormalities on physical examination;
- 2) History of seizures;
- 3) History of Hematological disorders;
- 4) Myocardial infarction within 6 months;
- 5) Current pregnancy or lactation, or inadequate contraception in girls of childbearing potential;
- 6) Current or recent (past 3 months) DSM-5 substance abuse or dependence;
- 7) Illegal substance use within 2 weeks of study initiation;
- 8) Previous treatment with Glutathione;
- 9) Current treatment with N-acetylcysteine, milk thistle, Vitamin C, Vitamin B, Grape Seed Extract, Amino Acids, or Zinc (known to interfere with Glutathione level)
- 11) Current treatment with Dextromethorphan, D-cycloserine, Amantadine, Memantine, Lamotrigine or Riluzole (known to have glutamatergic properties)
- 12) Asthma (given this is rare, but possible worsening of asthma symptoms due to Glutathione)

Assessments:

Existing Data

Before beginning Glutathione, all subjects will have a psychiatric, medical, and family history evaluation completed as part of their standard clinical care.

New Data Collection

At the screening visit, all subjects will receive a physical examination. For all subjects, at the initial visit, blood work will be obtained for a baseline Glutathione level. Glutathione level will also be obtained at study completion. Total amount of blood to be obtained will be 4 teaspoons. PI will obtain neuropsychological evaluations report if it is available.

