24 male and female outpatients aged 4-17 with a primary diagnosis of Autism Spectrum Disorder.

-Note on sample size: The sample size is low due to this being a pilot feasibility study and the primary aim of the study is not to examine the effectiveness of oral glutathione as a treatment but rather examine the functionality of providing oral glutathione on the blood level, the data will likely be used for future studies on treatment or grant applications. There also is no external sponsor, therefore internal funding limits the number of subjects.

Participant Exclusion:

For this study, children under the age of 4 and adults over the age of 17 will be excluded. The rationale for this is that the study population of interest are pediatric subjects in the children and adolescent age ranges.

Data Analysis:

Primary analyses will be intent-to-treat with last observation carried forward. Changes in the blood level of glutathione will be the primary outcome measure. For both primary and secondary measures, random regression analysis will be conducted using the MIXREG program

Demographic and baseline visit characteristics of the Glutathione treatment patients will be documented. Primary and secondary measures will be examined using analysis of variance modeling analyses (SPSS). The difference in the overall level of posttreatment values, the main effect for treatment, will be the test of primary interest. Analyses will be performed on all available data by the use of an intention-to-treat population (last observation carried forward). All patients who return for at least 1 follow-up visit will be included in the intention-to-treat population. Effect sizes will also calculated using the Cohen effect size index d. A d of 0.2 is considered a small effect size, 0.5 is medium, and 0.8 is large. Partial eta squared (η 2), which is the proportion of the effect + error variance that is attributable to the effect, will be calculated. Interpretation of η 2 is that greater than 0.2 is a large effect size, greater than 0.1 is a medium effect size, and greater than 0.05 is a small effect size.

The CGI severity scale will be used to assess clinically significant change after treatment. For someone to have a clinically significant change, her or his final CGI severity score had to be less than the cutoff score, and her or his change from baseline had to be greater than the reliable change index

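### The named primary test, a treatment main effect on post-treatment values, cannot be computed in a one-arm trial and leaves out the baseline draw that the primary outcome needs

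*Combined protocol and SAP*

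**What the plan says.** The design has one arm. Project Goals states that "Twenty-four subjects with ASD will receive 12 weeks of oral Glutathione reduced", and Methods describes an open-label trial with "treatment of oral Glutathione in 24 subjects with ASD". The Procedure section repeats this. No control group or comparator appears anywhere.

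The question is about change. Aim 1 is "To determine whether Glutathione given over a 12-week period increases plasma Glutathione level in a sample of 24 children", and Data Analysis states: "Changes in the blood level of glutathione will be the primary outcome measure". The data for it are two draws. New Data Collection and Safety Assessments both give a baseline level at the initial visit, and New Data Collection adds that "Glutathione level will also be obtained at study completion".

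For the model, Data Analysis says that for primary and secondary measures "random regression analysis will be conducted using the MIXREG program". Its next paragraph says the same measures will be examined by analysis of variance in SPSS. Neither statement gives model terms, factors or a contrast. The only sentence that picks out a primary test is: "The difference in the overall level of posttreatment values, the main effect for treatment, will be the test of primary interest".

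**The concern.** A main effect for treatment compares at least two treatment conditions, and among post-treatment values in this trial there is only one. The sentence also restricts attention to values after treatment, whereas the outcome and Aim 1 both need the value before it.

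Two things are at stake. First, an analyst cannot follow the sentence and would have to choose another test once the data are in, from two named approaches that have no stated contrast. Second, if a before-after change were reported under this wording, it would be labelled a treatment effect. With one arm, treatment cannot be separated from the passage of time.

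**Working it through.** The protocol gives no power or precision figure to reproduce. It justifies 24 subjects by pilot status and internal funding. The check is therefore on what the design can estimate.

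**Inputs**
- Subjects: 24, all on glutathione (Project Goals, Methods, Procedure).
- Glutathione draws per subject: 2, at the initial visit and at study completion (New Data Collection, Safety Assessments).
- Planned values: 24 × 2 = 48.

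**Step 1: the test as written.** Use post-treatment values only, with an intercept column and a treatment column. Treatment equals 1 for all 24 subjects, so the two columns are identical. The matrix has rank 1 out of 2 columns.
- df for treatment = rank with treatment − rank without = 1 − 1 = 0.
- Values used: at most 24 of 48, none from baseline.

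The only hypothesis left on these values is that their mean equals some fixed number, which says nothing about change.

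**Step 2: the weight bands.** The two regimens under Investigational Agent do form groups, but both receive glutathione and they differ in body weight by construction. Comparing them would not test whether the level rises.

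**Step 3: the contrast the outcome needs.** Use both draws, with one column per subject and a time column (baseline = 0, end = 1).
- Subject columns: rank 24.
- Adding time: rank 25, so df for time = 25 − 24 = 1.
- Error df = 48 − 25 = 23.

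**Step 4: treatment coded as off at baseline and on at the end.** This column is identical to time. The rank stays at 25, so treatment adds 25 − 25 = 0 df beyond time. What is estimated is the change over time, whichever label it carries.

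**Step 5: precision of the corrected test, for context only.** The assumptions are a two-sided 5% level, 24 complete pairs, and results in units of the SD of change, because the documents give no alpha, SD or target change.
- 95% CI half-width = t(0.975, 23)/√24 = 2.069/4.899 = 0.42.
- Power at a mean change of 0.60, from the noncentral t with 23 df and noncentrality 0.60 × 4.899 = 2.94: 0.804, or about 80%.
- With 20 complete pairs (an assumed loss of 4), the half-width is 0.47 and the change detectable with 80% power is 0.66.

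These figures describe the repaired test. They do not measure the size of the defect.

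**The case against.** The strongest reply is that the 0 df result depends on a literal reading. If treatment means on-treatment against baseline, as the stated outcome, Aim 1 and the two draws all suggest, the effect is an ordinary repeated-measures term with 1 and 23 df. The note on the ABC also speaks of setting end results against baseline. That is probably what the authors meant, and it can be computed. But this reading has to ignore the restriction to post-treatment values and supply a factor that no section defines. It also leaves the treatment label on what is a time effect.

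A second reply is that the sentence covers secondary measures too, and that an overall post-treatment level suits scales rated at several visits better than a single end draw. That does not help: at every post-baseline visit, treatment still has one level.

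A third is that this is a pilot, that a sentence repairs it, and that calling it essential overstates it. The repair is indeed cheap and Aim 1 remains answerable. Pilot status explains the sample size, but not a primary test that cannot be run on an outcome the plan itself calls primary.

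A fourth concerns the remedy, and part of it stands. With complete pairs, the paired t-test and the repeated-measures ANOVA are the same test. The random-intercept time effect agrees with them as long as the estimated subject variance is not zero. Which one is called primary is then largely preference; what matters is naming the contrast. The methods can differ when an end draw is missing, and that needs a decision of its own.

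**Conclusion.** The concern holds. As written, the designated primary test has 0 df for treatment, uses at most half of the planned glutathione values, and contradicts the outcome stated in the same section. This rests only on the one-arm design, the two-draw schedule and the wording of the sentence, with no assumption about effect size or variance.

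The conclusion is limited to the mismatch between the named test and the design and outcome. The data collection is adequate for Aim 1, and no bias in the estimated change is claimed. Because it affects the primary test, it should be corrected before the analysis starts.

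**What to change.** In Data Analysis, replace the sentence with wording such as:

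> *The primary test is the mean within-subject change in glutathione from the Visit 1 draw to the end-of-study draw, tested with a paired t-test and reported with a 95% confidence interval and the number of complete pairs; the MIXREG time effect is supportive.*

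- State the significance level and whether the test is one- or two-sided, since the protocol gives neither.
- If the SPSS analysis of variance of this outcome is kept, mark it as supportive too.
- Remove the reference to a treatment main effect, and describe the result as change over time on open-label glutathione.
- Decide separately how a missing end draw is handled. With only two draws, carrying the last observation forward puts the baseline value at the end and sets that subject's change to zero. The wording above does not settle this.

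The cost is one or two sentences of text, with no new data, patients or procedures.

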The following instruments will be completed at each visit throughout the study: 1) Aberrant Behavior Checklist [ABC], a 58-item parent report subjective scale used for assessing problem behavior in subjects with intellectual and developmental disabilities; 2) Social Responsiveness Scale [SRS], a 65-item parent report questionnaire designed to use with children ages 4-17, providing age- and gender-referenced ranges and assessing social deficits pertaining to autism and

Page 9 of 17 IRB19-0017 Version 2; date: 4/11/19 other domains; and 3) the Clinical Global Impression scale [CGI]; 7 point scale to measure symptom severity. Also, readings of patients' heart rates and blood pressures will be obtained; and assessment of side effects will be done at each visit.

Note on ABC and SRS:

The ABC is a standardized scale used for assessing problem behaviors in subjects with developmental and intellectual disabilities. The items are divided into five subscales: 1) Irritability; 2) Lethargy/Social Withdrawal; 3) Stereotypic Behavior; 4) Hyperactivity; and 5) Inappropriate Speech. High scores are indicative of severe behavioral symptoms. The ABC will be used to track the subjects' problem behaviors and difficulties over the course of the study. The severity of the subjects' problem behaviors must be assessed and examined its relationship with a baseline blood level of glutathione. In addition, by using this scale, we can observe the overall effect of oral Glutathione on problem behaviors, especially comparing the end results to the baseline.

The SRS is being used for the same purpose, although it is being used for secondary outcome measures. It is a parent report questionnaire designed for use with children aged 4-17 and provides age- and gender-referenced, as well as raw scores for the following domains: total score (reflecting severity of social deficits pertaining to autism); receptive, expressive, cognitive and motivational aspects of social behavior; and autistic preoccupations. High scores are also indicative of severe behavioral symptoms.

Note on additional measures:

Clinical Global Impression (CGI) (Severity) scale will be used by the clinician to assess overall severity of problem behaviors in Autism Spectrum Disorder subjects at baseline. This will be used as a secondary outcome measure over the course of the study and relates to Aim #1.

Study Population/Sample Size

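### For ABC, SRS and CGI, the overall-level test with LOCF mixes titration ratings with full-regimen ratings and does not give the end-versus-baseline change the protocol stresses

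*Combined protocol and SAP*

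**What the plan says.** **Visits.** The Methods section states: "Subjects will be seen every two weeks for the first month and then every four weeks for the remaining two months", and continues "with one final visit at the end of the study for a total of 5 visits". With the dosing calendar this gives Weeks 0, 2, 4, 8 and 12. The data-collection table instead shows a screening column plus Visits 1 to 6, with no weeks attached. ABC, SRS and CGI are rated at every visit.

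**Dose.** Under Investigational Agent, children at 40 kg or less take "500 mg by mouth twice a day for two weeks, then 1000 mg by mouth twice a day for ten weeks". Heavier children have two two-week steps, "then 1000 mg by mouth each morning and 2000 mg by mouth every afternoon for eight weeks". The section adds: "Dosages will be increased based on tolerability and the monitoring of any potential GI side effects as determined by the investigator".

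**Analysis.** Data Analysis names random regression (MIXREG) for primary and secondary measures, then analysis of variance for the same measures, with this target: "The difference in the overall level of posttreatment values, the main effect for treatment, will be the test of primary interest". It applies LOCF and admits any child with one follow-up visit. It does not say which visits enter the overall level or how they are weighted. The CGI rule for clinically significant change, in the same section, uses the final score.

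**Purpose of the ratings.** The Note on ABC and SRS says of the ABC that "we can observe the overall effect of oral Glutathione on problem behaviors, especially comparing the end results to the baseline", and gives the SRS the same purpose as a secondary measure.

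**The concern.** Ratings are closest together while the dose is still rising. An equal-weight average over post-baseline visits therefore gives the titration weeks more weight than their share of treatment time, and describes neither Week 12 nor the full regimen. LOCF adds to this, because a child who leaves after Week 2 contributes a score taken on 1000 mg/day at every later visit.

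The behavioural estimate and its effect sizes are at stake. Cohen's d and partial eta squared are to be calculated, and the sample-size note expects the data to support later studies or grant applications. A d averaged over titration visits could be read there as the change after 12 weeks. The CGI data would also be judged on two quantities: the overall level in the stated test and the final score in the clinically-significant-change rule.

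**Working it through.** **1. Check the calendar against the plan's own figure.** The study-drug count for the heavier group is 2×14 + 4×14 + 6×28 + 6×28 = 28 + 56 + 168 + 168 = 420, which matches "total per subject: 420 pills"; 420 × 24 = 10,080 also matches. The intervals are therefore 14, 14, 28 and 28 days, with post-baseline ratings at Weeks 2, 4, 8 and 12.

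**2. Share of ratings below the full regimen.** Each rating is assigned the dose taken in the interval before it.

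| Group | Daily dose before Weeks 2, 4, 8, 12 (mg) | Ratings below full | Time below full |
|---|---|---|---|
| Over 40 kg | 1000, 2000, 3000, 3000 | 2/4 = 50% | 4/12 = 33% |
| 40 kg or less | 1000, 2000, 2000, 2000 | 1/4 = 25% | 2/12 = 17% |

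If the table's Visit 6 is a fifth post-baseline rating on the full regimen, the rating shares become 2/5 = 40% and 1/5 = 20%. The documents give no weight mix.

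**3. Pooled effect as a fraction of the full-dose effect.** The documents give no behavioural dose-response or time course, so every shape here is an assumption.

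- Effect proportional to dose: (1000 + 2000 + 3000 + 3000)/(4 × 3000) = 0.75 over 40 kg; (1000 + 2000 + 2000 + 2000)/(4 × 2000) = 0.875 at 40 kg or less.
- Effect only on the full regimen: 2/4 = 0.50 and 3/4 = 0.75.
- Linear growth over 12 weeks, relative to Week 12: (2 + 4 + 8 + 12)/4/12 = 0.54.
- Approach to a plateau, effect 1 − 2^(−t/h) at week t, relative to Week 12: 0.81 for half-time h = 2 weeks, 0.69 for 4, 0.64 for 6.

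**4. How much is due to uneven spacing?** Weighting by time instead of by visit gives (2×1000 + 2×2000 + 8×3000)/(12 × 3000) = 0.83 over 40 kg and (2×1000 + 10×2000)/(12 × 2000) = 0.92 at 40 kg or less. Spacing explains (0.83 − 0.75)/0.25, about one third, and (0.917 − 0.875)/0.125, also one third. The rest comes from including titration ratings at all.

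**5. LOCF.** If 20% leave after Week 2 (assumption) and the effect is dose-proportional, the Week 12 value itself falls to 0.8 + 0.2 × 1/3 = 0.87 over 40 kg and 0.8 + 0.2 × 1/2 = 0.90 at 40 kg or less. A Week 12 contrast that keeps LOCF does not remove the problem.

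**6. Precision.** Assume a full-dose change of 0.4 SD, dose-proportional effect, equal correlation 0.5 between visits, two-sided 5% and all 24 children in one weight group. The change from baseline to a mean of k visits has SD √[(1 − 0.5)(1 + 1/k)]; power is from the noncentral t.

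| Group | Four-visit average | Week 12 only | Mean of full-dose visits |
|---|---|---|---|
| Over 40 kg | 43% | 47% | 58% |
| 40 kg or less | 55% | 47% | 63% |

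At correlation 0.8 the rows are 80%, 84%, 93% and 91%, 84%, 95%, in the same order.

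**The case against.** **Equal pooling is not stated.** The text never says that visits count equally, and posttreatment could mean the value at the end of treatment. Random regression, the final-score CGI rule and the stress on end results all point elsewhere, and a main effect for treatment has no comparator in one arm. This stands in part: averaging is the natural reading of an overall level, but it remains a reading. If it is not the intended one, the behavioural contrast is undefined, and the same sentence needs rewriting.

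**A reader might infer that any behaviour change is diluted.** The documents do not support that. Dilution needs an effect that grows with dose or time. Ratings are open-label and largely by parents, so an early expectancy response that fades would make the average larger than the Week 12 change.

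**A reader might infer that full-dose ratings come only every four weeks in all children, or that the visit spacing is the main cause.** Neither holds. At 40 kg or less the planned full dose starts at Week 2, so three of four ratings are on it and the first comes two weeks later. Spacing explains about a third of the dose-proportional shortfall.

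**A reader might infer that the main result or the power is compromised.** Blood glutathione is drawn at baseline and at completion only, so there is nothing to pool, and the sample-size note says effectiveness is not the primary aim. Averaging also reduces noise: at 40 kg or less the four-visit average has more power than Week 12 alone in the scenario above. The case rests on estimating the stated quantity, not on power.

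**Conclusion.** The point holds for ABC, SRS and CGI only. Read as an average over post-baseline visits, the stated test draws 50% of its ratings over 40 kg and 25% at 40 kg or less from below the full regimen (40% and 20% if Visit 6 is an extra full-dose rating), against 33% and 17% of treatment time. These are planned shares; because dose increases depend on tolerability, the actual shares could be higher. LOCF with the one-follow-up entry rule lets a Week 2 rating on 1000 mg/day stand as Week 12. The result does not match the end-versus-baseline comparison the protocol stresses.

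The size and direction of any distortion are conditional. If the effect grows with dose or time, the average understates the end-of-treatment change, for example to 0.75 (over 40 kg) and 0.875 (40 kg or less) of the full-dose effect if dose-proportional. An early expectancy response could reverse this. The primary outcome is not affected by the pooling.

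**What to change.** In Data Analysis, for ABC, SRS and CGI:

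- Replace the LOCF-based overall-level test with the change from baseline (Visit 1) to Week 12, taken as a contrast from the random regression already planned.
- Fit the model to observed ratings, without LOCF, with time as visit categories or as actual weeks. Visit categories impose no shape on the time course.
- Report earlier visits descriptively, labelled with the dose in use.
- Report the mean of the full-dose visits from the same model as a supportive estimate.

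Reconcile the 5-visit text with the table's Visits 1 to 6, so that Week 12 names one visit. Reconcile also the two weight-group headings in the dosing calendar, which both include a child of exactly 40 kg; otherwise that child's dose label is ambiguous.

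**Cost.** Wording only: no new visits, data or patients. A single-visit contrast is noisier than a four-visit average. With complete data and visit categories it equals the plain mean change at Week 12, so the model recovers no precision from the other visits. Power may fall, mainly at 40 kg or less (55% to 47% in the scenario above). Dropping LOCF means relying on the model's assumption that missing ratings are explained by the observed ones, so dropouts should be listed with their last dose and reason.
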